## 8 STUDY OBJECTIVES

The primary objective of this study is to evaluate executive function in adult subjects with PKU who are participating in Study 165-302, as measured by selected CANTAB tasks.

The exploratory objective of this study is to evaluate patient self perception in adult subjects with PKU who are participating in Study 165-302 for use as anchors in the interpretation of change over time in measures of inattention and mood.

## 9 INVESTIGATIONAL PLAN

### 9.1 Overall Study Design and Plan

This is a Phase 3 substudy enrolling approximately 100 subjects, aged  $\geq 18$  to  $\leq 70$  years old, with PKU who are concurrently treated with BMN 165 or placebo in Part 2 and BMN 165 in Part 4 of Study 165-302. No study drug is administered as part of this study. For this study, subjects will be asked to perform computer-based assessments (CANTAB) that assess executive function (specifically, attention, working memory, cognitive flexibility) and to answer questions about their current state of self perception (subject global assessment comprised of seven questions).

After providing informed consent, subjects undergo screening evaluations to determine study eligibility. Study drug dosing should continue without interruption as part of subject participation in Study 165-302. Screening assessments may be completed within 14 days before Day 1 or on Day 1 of this study. If screening assessments are performed on Day 1, they must be performed before any other Day 1 assessments.

Executive function will be assessed using a selected set of three tasks from the CANTAB tool (Rapid Visual Processing [RVP], Spatial Working Memory [SWM], and Stop Signal Task [SST]). Each subject's self perception of their current state will be measured using a subject global assessment questionnaire that contains seven questions about current state perception of attention, energy level, tiredness, confusion, sadness, anger and tension.

Subjects who discontinue from study drug in Part 2 or Part 4 of 165-302 will be asked to continue their participation in this study.

Assessments for this study must be performed at the same scheduled clinic visit of Part 2 and Part 4 of Study 165-302. Assessments for evaluation of executive function will be performed as presented in Table 9.1.1.

**Table 9.1.1: Schedule of Events**

Event or Assessment a	Screening b	Part 2: Week 1 of Day 1 of Study 165-302 c (Baseline)	Part 2: Week 8 of Study 165-302	Part 4: Week 9 of Study 165-302	Part 4: Week 25 of Study 165-302	Part 4: Week 49 of Study 165-302 d	Early Termination e
	Day -14 to Day 1	± 1 day	- 5 days of Day 56	± 3 days	± 7 days	± 7 days	
Informed consent	X						
Demographics (date of birth)	X						
CANTAB practice session		X					
Subject global assessment questionnaire f		X	X	X	X	X	X
CANTAB		X	X	X	X	X	X

ADHD-RS, Attention Deficit Hyperactivity Disorder Rating Scale (investigator-rated with adult prompts); CANTAB, Cambridge Neuropsychological Test Automated Battery; POMS, Profile of Mood States.

All scheduled visits are in the study clinic. Assessments for this study must be performed at the same scheduled clinic visit performed for Study 165-302. Adverse event reporting and data collection must be performed in Study 165-302. For all visits after the Baseline Visit, assessment should be performed in the following order: ADHD/POMS of Study 165-302, subject global assessment, CANTAB, and study drug administration in Study 165-302.

aNo study procedures or assessments are to be performed before informed consent is obtained. After written informed consent, screening assessments must be within 14 days before Day 1 of this study.

bScreening assessments may be completed within 14 days before Day 1 or on Day 1 of this study. If screening assessments are performed on Day 1, they must be performed before any other Day 1 assessments.

cAssessments to establish baseline must be performed in the following order: CANTAB practice session, ADHD and POMS of Study 165-302, subject global assessment, CANTAB (Part 2, Day 1 of Week 1), and study drug administration in Study 165-302.

dThis is the last scheduled visit for this study.

eThe visit should be performed within 8 weeks after the last scheduled visit.

fMust be performed before administration of the CANTAB in this study.

## 9.2 Discussion of Study Design, Including Choice of Control Group

A discussion of the chosen study design is provided in Section 7.1.

## 9.3 Selection of Study Population

Subjects at least 18 to  $\leq 70$  years old with PKU who are concurrently participating in Study 165-302 have been selected for this study. Additional details regarding subjects who may or may not be eligible for participation are provided in Section 9.1. Rationale for selection of these subjects for study participation is provided in Section 7.1. Additional criteria for study participation are presented in Section 9.3.1 and Section 9.3.2.

### 9.3.1 Inclusion Criteria

Individuals eligible to participate in this study must meet all of the following criteria:

- Are currently participating in Part 1 of Study 165-302 and meet the criteria for participation in Part 2 of 165-302
- Are willing and able to provide written, signed informed consent after the nature of the study has been explained and prior to any research-related procedures.
- Have the ability to complete the CANTAB and subject global assessment.
- Are willing and able to comply with all study procedures.

### 9.3.2 Exclusion Criteria

Individuals who meet the following exclusion criterion will not be eligible to participate in the study:

- Any condition that, in the view of the investigator, places the subject at high risk of poor compliance or terminating early from the study

### 9.3.3 Removal of Subjects from Treatment or Assessment

Subjects may withdraw their consent to participate in this study at any time without prejudice. The investigator must withdraw from the study any subject who requests to be withdrawn. Subject participation in the study may be discontinued at any time at the discretion of the investigator and in accordance with his or her clinical judgment. Procedures listed for the Early Termination visit should be performed (refer to Section 12.3.1.3 and Section 12.3.2.4).

BioMarin must be notified of all subject withdrawals as soon as possible. BioMarin also reserves the right to discontinue the study at any time for either clinical or administrative

reasons and to discontinue participation by an individual investigator or site for poor enrollment or noncompliance.

Reasons for which the investigator or BioMarin may withdraw a subject from the study include, but are not limited to, the following:

- Subject does not adhere to study requirements specified in the protocol
- Subject was erroneously admitted into the study or does not meet entry criteria
- Subject is lost to follow-up

If a subject fails to return for scheduled visits, a documented effort must be made to determine the reason. If the subject cannot be reached by telephone, a certified letter will be sent to the subject requesting contact with the investigator. This information should be recorded in the study records.

Before enrollment in the study, the investigator (or designee) must explain to each subject that the subject's protected health information obtained during the study may be shared with the study sponsor, regulatory agencies, and the IRB/IEC. It is the responsibility of the investigator (or designee) to obtain written permission to use protected health information per country-specific regulations, such as HIPAA in the United States, from each subject.

If permission to use protected health information is withdrawn, it is the responsibility of the investigator to obtain a written request to ensure that no further data will be collected from the subject. The subject will then be terminated from the study.

If study drug is discontinued in Study 165-302 before study completion, the investigator will ask the subject to remain in this study (165-303) to continue study visits and assessments, provided the subject's health, safety, and welfare are not detrimentally affected.

#### **9.3.4 Subject Identification and Replacement of Subjects**

Subjects are not replaced in this study. Each subject is assigned a unique subject identifier, which is on all case report form (CRF) pages. In legal jurisdictions where use of initials is not permitted, a substitute identifier is used.

#### **9.3.5 Duration of Subject Participation**

Following a screening period of up to 14 days, subjects will be assessed for 63 weeks as part of this study.

## 9.4 Treatments

### 9.4.1 Treatments Administered

No study drug is administered in this study. After the screening period, subjects will be asked to complete assessments and procedures for this study for 63 weeks.

### 9.4.2 Return and Disposition of Clinical Supplies

All study-related materials should be stored, inventoried, reconciled, and returned according to applicable state and federal regulations and study procedures.

## 9.5 Efficacy Variables

The CANTAB battery of tasks are computer-based tasks that are designed for GCP-compliant studies, and each electronic data capture build meets FDA regulations for computerized systems used in clinical trials and 21 CFR Part 11. For this study, three computerized CANTAB tasks, the RVP, SWM, and SST, have been selected for evaluation. These CANTAB tasks were reviewed for relevance and feasibility by a panel of neuropsychologists working with PKU patients. The panel reviewed the systematic literature review and meta-analysis and provided input from their clinical and research experience. Each CANTAB task is administered using a standardized touch-screen tablet computer, provided by Cambridge Cognition Ltd. The selected CANTAB tasks are considered to have the sensitivity for detecting changes in the neurocognitive functional domains (Bilder, 2014, Poster) relevant for adults with PKU: sustained attention, inhibitory control, and working memory:

- The RVP task measures sustained attention. In this task, a series of random digits continuously appears in the middle of the screen. Subjects are asked to recognize a specific sequence of digits and are asked to press a button on the screen whenever this specific sequence of digits appears within this series of continuous digits.
- The SST task measures inhibitory control and cognitive flexibility. The SST is a 2-part task. During part 1, an arrow appears on the screen and subjects are asked to press an arrow button on the screen corresponding with the direction of the arrow displayed. During part 2 of the task, subjects follow the same instructions as in part 1; however, they are asked to withhold their response (do not press an arrow button) if they hear an auditory signal (beep) when the arrow is displayed.

- The SWM task measures visuospatial working memory. During this task, a number of boxes appears on a screen. The objective of the task is to find a token under a box and to place this token in a designated area. There is only one token under one box during each round and the location of the token rotates in each round to a different box, other than a box within which the token was found in previous rounds. The subject is therefore asked to remember which boxes previously contained tokens so as to better the chances and speed of finding tokens under boxes which did not previously contain tokens.

The subject global assessment is a paper-based, seven-item questionnaire that will be administered to subjects as part of this study; subjects will be asked to rate their current-state perceptions of attention (very poor, poor, fair, good, excellent), energy level (very low, low, moderate, high, very high), tiredness (extreme tiredness, a lot of tiredness, some tiredness, a little tiredness, no tiredness at all), confusion (extreme confusion, a lot of confusion, some confusion, a little confusion, no confusion at all), sadness (extreme sadness, a lot of sadness, some sadness, a little sadness, no sadness at all), anger (extreme anger, a lot anger, some anger, a little anger, no anger at all), and tension (extreme tension, a lot of tension, some tension, a little tension, no tension at all).

The Schedule of Events tables in Section 9.1 outline the timing of required events and assessments.

### 9.5.1 Primary Efficacy Variable

The primary efficacy variables (as assessed by the CANTAB) are as follows:

- RVP mean latency
  - RVP mean latency is the mean response latency during assessment sequence blocks where the subject responded correctly (milliseconds).
- SWM between errors
  - SWM between errors measures the total number of times the subject revisits a box in which a token has previously been found in the same problem (calculated for assessed problems only).
- SST stop signal delay
  - SST stop signal delay is the length of time between the go stimulus and the stop stimulus at which the subject is able to successfully inhibit their response on 50% of trials.

The primary efficacy endpoints are these variables collected in Part 2, Week 8.

### 9.5.2 Secondary Efficacy Variables

The secondary efficacy variables (as assessed by the CANTAB) are as follows:

- RVP A prime
  - RVP A prime represents the signal detection measure of sensitivity to the target, regardless of response tendency (the expected range is 0.00 to 1.00; bad to good). In essence, measure of how good the subject is at detecting target sequences.
- SWM strategy
  - For assessed problems with six boxes or more, SWM strategy is the number of distinct boxes used by the subject to begin a new search for a token (within the same problem).
- SST proportion of successful stops
  - SST proportion of successful stops measures the proportion of completed stop trials that were successful stops.

Each secondary efficacy endpoint will be analyzed similar to the primary efficacy endpoints at Part 2, Week 8.

### 9.5.3 Exploratory Efficacy Variables

Exploratory endpoints are as follows:

### 9.5.4 Safety Variables

In this study, safety will be determined from evaluation of AEs in Study 165-302.

## **10 REPORTING ADVERSE EVENTS**

Subjects participating in this study will also be concurrently participating in Study 165-302. AEs relative to any study drug or study procedure performed as part of Study 165-302 or this study should be reported for Study 165-302.

**11 APPROPRIATENESS OF MEASUREMENTS**

**11.1 CANTAB and Subject Global Assessment**

A discussion of executive function and its relationship with PKU is provided in Section 7.1.

A description of the CANTAB tools and subject global assessment questionnaire administered in this study are also provided in Section 9.5.

## 12 STUDY PROCEDURES

Assessment of AEs and concomitant medications should be performed as part of Study 165-302. Subjects who discontinue from study drug early in Study 165-302 will be asked to continue to perform the visit assessments of this study until study completion (refer to Section 9.3.3).

### 12.1 Prestudy

An ICF must be signed and dated by the subject (or legal guardian if appropriate), investigator (or designee), and witness before any study-related procedures are performed.

### 12.2 Screening Visit (Days -14 to Day 1)

Once written informed consent has been obtained, subject demographic information (date of birth) should be recorded at the Screening Visit. Screening assessments may be completed within 14 days before Day 1 or on Day 1 of this study. If screening assessments are performed on Day 1, they must be performed before any other Day 1 assessments.

### 12.3 Study Visits

All assessments should be performed at approximately the same time of day for each visit (refer to Section 12.3.1 [Part 2] and Section 12.3.2 [Part 4]).

#### 12.3.1 Part 2

The subject global assessment and CANTAB should be administered in the clinic at the same time as the visits performed for Part 2 of Study 165-302.

##### 12.3.1.1 Part 2: Week 1 of Day 1 of Study 165-302 (Baseline [± 1 day])

Assessments should be performed in the following order:

- CANTAB practice session,
- ADHD and POMS of Study 165-302,
- Subject global assessment,
- CANTAB, and
- Study drug administration in Study 165-302

**12.3.1.2 Part 2: Week 8 of Study 165-302 (– 5 days of Day 56)**

Assessments should be performed in the following order:

- ADHD and POMS of Study 165-302,
- Subject global assessment,
- CANTAB, and
- Study drug administration in Study 165-302

**12.3.1.3 Early Termination**

The Early Termination Visit should be performed within 8 weeks of the last scheduled visit. Assessments should be performed in the following order if a subject terminates from the study early during Part 2:

- ADHD and POMS of Study 165-302,
- Subject global assessment,
- CANTAB

**12.3.2 Part 4**

The subject global assessment and CANTAB should be administered in the clinic at the same time as the visits performed for Part 4 of Study 165-302.

**12.3.2.1 Part 4: Week 9 of Study 165-302 (± 3 days)**

Assessments should be performed in the following order:

- ADHD and POMS of Study 165-302,
- Subject global assessment,
- CANTAB, and
- Study drug administration in Study 165-302

**12.3.2.2 Part 4: Week 25 of Study 165-302 (± 7 days)**

Assessments should be performed in the following order:

- ADHD and POMS of Study 165-302,
- Subject global assessment,
- CANTAB, and
- Study drug administration in Study 165-302

**12.3.2.3 Part 4: Week 49 of Study 165-302 ( $\pm 7$  days)**

This is the last scheduled visit for this study. Assessments should be performed in the following order:

- ADHD and POMS of Study 165-302,
- Subject global assessment,
- CANTAB, and
- Study drug administration in Study 165-302

**12.3.2.4 Early Termination**

The Early Termination Visit should be performed within 8 weeks of the last scheduled visit. Assessments should be performed in the following order if a subject terminates from the study early during Part 4:

- ADHD and POMS of Study 165-302,
- Subject global assessment,
- CANTAB

### 13 DATA QUALITY ASSURANCE

BioMarin personnel (or designees) may visit the study site prior to initiation of the study to review with the site personnel information about the protocol and other regulatory document requirements; applicable randomization procedures; source document requirements; CRFs; monitoring requirements; and procedures for reporting AEs, including SAEs.

At visits during and after the study, a CRA will monitor the site for compliance with regulatory documentation, with a focus on accurate and complete recording of data on CRFs from source documents, adherence to protocol, and randomization (if applicable).

The designated clinical data management group will enter or transfer CRF data into a study database if applicable.

Data quality control and analysis will be performed by BioMarin (or a designee) based on a predefined analysis plan.

## **14 STATISTICAL METHODS AND DETERMINATION OF SAMPLE SIZE**

The Statistical Analysis Plan (SAP) will provide additional details on the planned statistical analysis. Unless otherwise stated, all analyses will be performed using SAS version 9.2.

### **14.1 Procedures for Accounting for Missing, Unused and Spurious Data**

Because the completeness of the data affects the integrity and accuracy of the final study analysis, every effort will be made to ensure complete, accurate and timely data collection and, therefore, avoid missing data. If study drug is discontinued in Study 165-302 before completion of 165-302, the investigator will ask the subject to remain in this study (165-303) to continue the visits and assessments of this study, provided the subject's health, safety, and welfare are not detrimentally affected.

Missing data will be imputed for the primary and secondary endpoints. Additional details regarding missing data will be provided in the SAP.

### **14.2 Analysis Populations**

The intent-to-treat (ITT) population will consist of all subjects who are enrolled into the study with at least one executive function assessment.

### **14.3 Primary Efficacy Analysis**

No multiplicity adjustment will be performed for multiple primary efficacy endpoints. Each primary efficacy endpoint will be compared between High Active Group (Study 165-302) and the pooled Placebo Groups (Study 165-302) and between the Low Active Group (Study 165-302) and the pooled Placebo Groups (Study 165-302) using Analysis of Covariance Model (ANCOVA) with treatment and baseline assessment as factors. For this study, baseline is defined as the assessment collected during the Part 2, Day 1 visit (predose) of Study 165-302.

The primary efficacy endpoints will also be summarized descriptively over time in Part 4 at Week 9, Week 25, and Week 49.

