
Study 165-302. Screening assessments may be completed within 14 days before Day 1 or on Day 1 of this study. If screening assessments are performed on Day 1, they must be performed before any other Day 1 assessments.
 
Executive function will be assessed using a selected set of three tasks from the CANTAB tool (Rapid Visual Processing [RVP], Spatial Working Memory [SWM], and Stop Signal Task [SST]). Each subject's self perception of their current state will be measured using a subject global assessment questionnaire that contains seven questions about current state perception of attention, energy level, tiredness, confusion, sadness, anger and tension. The subject global assessment and CANTAB tasks will be administered at the site at five time points during this study and must coincide with the time points in Part 2 and Part 4 of Study 165-302: upon entry into Part 2 (Day 1 of Week 1), upon completion of Part 2 (Week 8) and at the Week 9, Week 25, and Week 49 visits of Part 4. The 165-302 study assessments (ADHD-RS and POMS) must be performed first, followed by the subject global assessment and then the CANTAB. The first study drug administration given in Part 2 of Study 165-302 should be given last, after the CANTAB. Subjects who discontinue from study drug in Part 2 or Part 4 of 165-302 will be asked to continue their participation in this study.
		

NUMBER OF SUBJECTS PLANNED: Approximately 100 subjects at selected sites are planned for enrollment into this study.
		

DIAGNOSIS AND ENTRY CRITERIA:
 
Individuals eligible to participate in this study must meet all of the following criteria:
 
 
• Are currently participating in Part 1 of Study 165-302 and meet the criteria for participation in Part 2 of 165-302
 
• Are willing and able to provide written, signed informed consent after the nature of the study has been explained and prior to any research-related procedures.
 
• Have the ability to complete the CANTAB and subject global assessment.
 
• Are willing and able to comply with all study procedures.
 
 
Individuals who meet the following exclusion criterion will not be eligible to participate in the study:
 
 
• Any condition that, in the view of the investigator, places the subject at high risk of poor compliance or terminating early from the study
 
		

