BioMarin Pharmaceutical Inc. is developing BMN 165 (pegvaliase; recombinant *Anabaena variabilis* phenylalanine ammonia lyase-PEG [rAvPAL-PEG]) as an enzyme substitution therapy to reduce blood Phe concentrations in patients with PKU. BMN 165 is a genetically modified cyanobacterium phenylalanine ammonia lyase enzyme (homologue of human phenylalanine hydroxylase [PAH]), expressed in *E. coli* and PEGylated after production to decrease immunogenicity. The BMN 165 clinical program evaluates the effect of BMN 165 on blood Phe levels and will characterize the relationship of blood Phe to other important clinical outcomes. Two Phase 3 studies of BMN 165, 165-301 (A Phase 3, Open-Label, Randomized, Multi-Center Study to Assess the Safety and Tolerability of an Induction, Titration, and Maintenance Dose Regimen of BMN 165 Self Administered by Adults With Phenylketonuria Not Previously Treated with BMN 165) and 165-302 (A Four-Part, Phase 3, Randomized, Double-Blind, Placebo-Controlled, Four-Arm, Discontinuation Study to Evaluate the Efficacy and Safety of Subcutaneous Injections of BMN 165 Self Administered by Adults with Phenylketonuria), are underway to assess the effect of BMN 165 on blood Phe levels, inattentiveness, hyperactivity/impulsivity, and mood (anger, anxiety, confusion,

depression, tiredness, and vigor) in adults with PKU. Additional evaluation of BMN 165 on other neurocognitive domains in adults with PKU will be performed with this Phase 3 substudy.

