3.5.2 Randomization Method

Randomization does not occur in this study; however, subjects enrolling in this study are treated based on the randomization criteria in Part 2 of Study 165-302. In Study 165-302, subjects were randomized (2:1) to receive 20 mg/day pegvaliase (20mg/day Active Group) or a matching placebo (20 mg/day Placebo Group). Subjects were also randomized (2:1) to receive 40 mg/day pegvaliase (40mg/day Active Group) or a matching placebo (40mg/day Placebo Group).

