4.2 Treatment Group Presentation

When analyzing data collected while subjects are in Part 2 of Study 165-302, the following treatment groups will be used for presentation:

- Pooled active group
- Pooled placebo group

When analyzing data collected while subjects are in Part 4 of Study 165-302, all subjects will be combined and an overall summary will be provided.

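### The SAP shows Part 2 only as pooled active and pooled placebo, so the separate result for each dose that the protocol planned is lost without a stated reason

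*Protocol*

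**What the plan says.** **Randomisation.** It takes place in the parent study. SAP 3.5.2: "Randomization does not occur in this study; however, subjects enrolling in this study are treated based on the randomization criteria in Part 2". The same section says that "subjects were randomized (2:1) to receive 20 mg/day pegvaliase (20mg/day Active Group) or a matching placebo (20 mg/day Placebo Group" and then that "Subjects were also randomized (2:1) to receive 40 mg/day pegvaliase (40mg/day Active Group) or a matching placebo (40mg/day Placebo Group". Protocol section 7 gives the parent title, which includes "Placebo-Controlled, Four-Arm, Discontinuation Study". Neither document says whether assignment to 20 or 40 mg/day was itself random.

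**Protocol analysis.** Section 14.3 and the synopsis plan two Week 8 contrasts for each primary endpoint. One is "compared between High Active Group (Study 165-302) and the pooled Placebo Groups (Study 165-302" and the other is "between the Low Active Group (Study 165-302) and the pooled Placebo Groups (Study 165-302". Both use an ANCOVA with treatment and baseline and no term for dose group. Section 14.4 treats the secondary endpoints in the same way. I read Low as 20 mg/day and High as 40 mg/day; the protocol does not define the labels.

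**SAP analysis.** Section 4.2 lists two groups for Part 2, a pooled active group and a "Pooled placebo group". Part 4 is one overall group. Sections 8.2.1 and 8.3.1 provide descriptive summaries, with no model or test.

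**Precedence.** Protocol 14.7 and SAP section 3 both say that the SAP governs where the two differ.

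**The concern.** The protocol asks a question about each dose, and the SAP answers a different one: active against placebo, averaged over doses. The two are equivalent only if the doses act alike on the CANTAB measures, and the planned tables give no means of checking that. A pooled change could come from both doses equally or from one dose alone, and the reader could not tell which. The change is also unexplained, so a reader comparing the documents cannot know whether the dose question was dropped for good reason or by oversight.

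A second question arises if the protocol's contrasts are restored or run later. Each sets one dose against placebo subjects from both dose groups, with no dose-group term. Whether that is sound depends on how the dose groups were formed.

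**Working it through.** The documents contain no figure to reproduce. The visible sample-size sections give no effect size, SD or power, so what follows is illustrative.

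**Inputs from the documents**
- Total N about 100 (protocol synopsis: "Approximately 100 subjects at selected sites are planned for enrollment into this study").
- 2:1 active to placebo at each dose (SAP 3.5.2).

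**Assumptions**
- Share *w* of subjects in the 20 mg/day group: 0.5, with a range of 0.3 to 0.7.
- Residual difference *D* between dose groups (40 minus 20) at Week 8 after baseline adjustment: 0.1 to 0.5 SD.
- SD = 1; two-sided 5% level where power is quoted.

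**Group sizes at *w* = 0.5.** Each dose group has 50 subjects: 33.3 active and 16.7 placebo. Pooled active is 66.7 and pooled placebo 33.3.

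**1. What the pooled contrast hides.** It estimates *w* × (20 mg effect) + (1 − *w*) × (40 mg effect). At *w* = 0.5, effects of 0.2 and 0.2 SD give 0.2. Effects of 0.4 and 0 SD also give 0.5 × 0.4 + 0.5 × 0 = 0.2. The SAP table would look the same in both cases.

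**2. Expected dose-group bias of the pooled contrast.** With 2:1 in both groups, the 40 mg/day share is (1 − *w*) among active and among placebo subjects alike. Bias = (1 − *w*)*D* − (1 − *w*)*D* = 0 at every *w*.

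**3. Expected bias of the protocol's dose contrasts, if dose group was not randomly assigned.**
- Low against pooled placebo: 0 − (1 − *w*)*D* = −(1 − *w*)*D*.
- High against pooled placebo: *D* − (1 − *w*)*D* = *wD*.

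At *w* = 0.5 these are −*D*/2 and +*D*/2:

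| *D* (SD) | Low | High |
|---|---|---|
| 0.1 | −0.05 | +0.05 |
| 0.2 | −0.10 | +0.10 |
| 0.3 | −0.15 | +0.15 |
| 0.5 | −0.25 | +0.25 |

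The signs are opposite, so the pattern would resemble a dose effect. For *w* from 0.3 to 0.7 the multiplier of *D* runs from 0.3 to 0.7. If dose group was randomly assigned, the expected *D* is 0 and so is the bias.

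**4. Precision at *w* = 0.5, SE = √(1/n₁ + 1/n₂).**
- Pooled active against pooled placebo: √(1/66.7 + 1/33.3) = 0.212 SD.
- The same effect with dose group as a factor: each dose group contributes a variance of 0.300² = 0.09, so √(0.25 × 0.09 + 0.25 × 0.09) = 0.212 SD. Nothing is lost.
- One dose against pooled placebo: √(1/33.3 + 1/33.3) = 0.245 SD.
- One dose against its own placebo: √(1/33.3 + 1/16.7) = 0.300 SD.
- Ratio of the last two: 0.300/0.245 = 1.22, so confidence intervals are about 22% wider.
- Power for a 0.5 SD effect: 53% with pooled placebo, 39% with own placebo. The difference detectable with 80% power is 0.69 against 0.84 SD. Over *w* = 0.3 to 0.7 the ranges are 0.64 to 0.79 and 0.71 to 1.09 SD.

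**The case against.** **A reader might infer that the protocol's dose contrasts are partly non-randomised**, because SAP 3.5.2 describes the two 2:1 allocations one after the other. The documents do not support that. The same sentences fit a single 2:1:2:1 randomisation to four arms, and the parent title speaks of a randomised four-arm study. In that case pooled placebo is a valid randomised comparator and the more precise one. The silence runs both ways: the SAP describes active-to-placebo allocation at each dose and says nothing about allocation between doses. The bias in step 3 is therefore conditional.

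**A reader might also infer that the planned analysis has an inflated type I error.** It does not follow. The SAP prevails and contains no test. Its only Part 2 comparison has no expected dose-group bias, and chance imbalance in a subset of about 100 is ordinary sampling variation. Nor does the SAP merge everything in Part 2: active and placebo stay separate, and only the doses are combined.

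**Pooling doses is a reasonable choice at this size.** This has force. At an equal split, the difference between the two dose effects, each against its own placebo, has SE √(0.300² + 0.300²) = 0.424 SD. Its 95% interval therefore extends about 1.96 × 0.424 = 0.83 SD either way, and four columns would reveal only a large disagreement. That limits what the columns can prove. It does not explain why a comparison named in the protocol appears in no table, when the SAP is descriptive and the data are already held.

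**Conclusion.** The point holds as one of lost information and unreconciled documents. The protocol plans a Week 8 result for each dose; the prevailing SAP reports none and gives no reason. Under the planned tables a disagreement between 20 and 40 mg/day could not be seen.

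The SAP's pooled contrast is not biased in expectation by dose group. This rests on the equal 2:1 ratios and not on any assumed split.

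The protocol's contrasts against pooled placebo are open to question only if assignment to dose group was not random. The bias would then be about *D*/2 in opposite directions at an equal split: 0.05 to 0.25 SD for an assumed residual *D* of 0.1 to 0.5 SD. If assignment was random, pooling placebo has no expected bias from this source. The documents do not settle which applies. N = 100 is the planned figure; the dose split, *D* and unit SD are assumptions.

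**What to change.** 1. In SAP 4.2, 8.2.1 and 8.3.1, present Week 8 values and changes from baseline for the four randomised groups (20 mg/day active, 20 mg/day placebo, 40 mg/day active, 40 mg/day placebo) beside the pooled groups. Cost: SAP wording and four table columns, with small placebo columns (about 17 each at an equal split) that must be read with that in mind.
2. State in SAP 3.5.2 how subjects were assigned to the 20 or 40 mg/day group in the parent study.
3. Reconcile protocol 14.3 with SAP 4.2 and 8.2.1. Say that the dose comparisons and the ANCOVA were dropped and why, or restore them.
4. If the ANCOVA is restored, include dose group as a factor with treatment and baseline for the pooled effect. Its SE stays about 0.21 SD. Restoring a model is a larger change than adding columns, since the SAP now has none.
5. If dose contrasts are also restored, let the answer to item 2 decide the comparator. If dose group was not randomly assigned, compare each dose with its own matching placebo and accept confidence intervals about 22% wider and, for a 0.5 SD effect, power of 39% instead of 53%. If it was randomly assigned, pooled placebo can stay, with that reason given.
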